11.3 VITAL SIGNS

Descriptive statistics for vital signs (systolic and diastolic blood pressures, heart rate, and weight) and changes from baseline values at each visit and at the end of the double-blind study period will be presented by treatment group.

Vital sign values will be considered PCS if they meet both the observed-value criteria and the change-from-baseline criteria listed in Table 11.3–1. The number and percentage of subjects with PCS postbaseline values will be tabulated by treatment group for the double-blind treatment period. The percentages will be calculated relative to the number of subjects with available baseline values and at least 1 postbaseline assessment for the treatment period. The numerator will be the total number of subjects with available baseline values and at least 1 PCS postbaseline value for the treatment period. A supportive tabular display of subjects with PCS postbaseline values will be provided, including SID, study center number, and baseline and all postbaseline (including non-PCS) values.

In addition, a tabular display showing all AEs that occurred in subjects who had PCS postbaseline vital sign values will be provided.

Shift tables from baseline to end of the double-blind study period for vital signs (systolic and diastolic blood pressures, pulse rate) will be presented by treatment group for the following categories: low, normal, and high

Table 11.3–1. Criteria for Potentially Clinically Significant Vital Signs

Vital Sign	Age	Gender	Flag	Criterion Value
Systolic blood pressure, mm Hg	9 to 45	Female or Male	High	> 140
Diastolic blood pressure, mm Hg	9 to 45	Female or Male	High	≥ 90
Heart rate, beats per minute	9 to 12	Female	High	> 121
			Low	< 50
	9 to 12	Male	High	> 112
			Low	< 49
	13 to 16	Female	High	> 118
			Low	< 48
	13 to 16	Male	High	> 110
			Low	< 42
	17 to 45	Female or Male	High	> 110
	17 to 45	Female or Male	Low	< 44

11.4 ELECTROCARDIOGRAM

Descriptive statistics for ECG parameters (heart rate, RR interval, PR interval, QRS duration, QT interval, and QTc) and changes from baseline values at each assessment time point to the end of the double-blind study period will be presented by treatment group. The QTc will be calculated using both the Bazett and Fridericia corrections.

Electrocardiographic parameter values are considered PCS if they meet or exceed the higher-limit PCS criteria listed in Table 11.4–1. The number and percentage of subjects with PCS postbaseline ECG values will be tabulated by treatment group for the double-blind treatment period. The percentages will be calculated relative to the number of subjects with available non-PCS baseline values and at least 1 postbaseline assessment for the treatment period. The numerator is the total number of subjects with available non-PCS baseline values and at least 1 PCS postbaseline value for the treatment period. A supportive tabular display of subjects with PCS postbaseline values will be provided, including SID, study center number, baseline, all postbaseline (including non-PCS) values, and change from baseline.

In addition, a tabular display showing all AEs that occurred in subjects who had postbaseline PCS ECG values will be provided.

A shift table from baseline to the end of the double-blind study in the Investigator's overall interpretation of the ECG will be presented by treatment group for the following categories: normal; abnormal, not clinically significant; abnormal, clinically significant. A tabular display showing subjects with postbaseline clinically significant ECG abnormalities according to the Investigator's overall interpretation will be provided.

Table 11.4–1. Criteria for Potentially Clinically Significant Electrocardiograms

Parameter	Unit	Higher Limit
QRS duration	msec	≥ 120
PR interval	msec	> 220 or < 110
QTc (QTcB or QTcF) interval	msec	> 500

QTc = QT interval corrected for heart rate.

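### SAP Table 11.4-1 flags QTc only above 500 msec, so no table described in the SAP counts, by arm, subjects with a lower raised QTc or a large rise from baseline

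*SAP*

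**What the plan says.** SAP 11.4 sets the rule: "Electrocardiographic parameter values are considered PCS if they meet or exceed the higher-limit PCS criteria" of Table 11.4-1. That table has three rows: QRS of 120 msec or more, PR above 220 or below 110 msec, and "QTc (QTcB or QTcF) interval" above 500 msec. None uses change from baseline.

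The by-arm count is of new cases: "The numerator is the total number of subjects with available non-PCS baseline values and at least 1 PCS postbaseline value for the treatment period". The subject display does show change from baseline, but only for subjects already flagged: "A supportive tabular display of subjects with PCS postbaseline values will be provided, including SID, study center number, baseline, all postbaseline". The adverse-event display is limited in the same way.

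The SAP has other ECG outputs:

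- Descriptive statistics for QTc under both the Bazett and Fridericia corrections, where "changes from baseline values at each assessment time point to the end of the double-blind study period will be presented by treatment group". SAP 11.0 lists the minimum and maximum among the statistics for continuous safety variables.
- A by-arm shift table of the Investigator's overall ECG interpretation, and a subject display: "A tabular display showing subjects with postbaseline clinically significant ECG abnormalities according to the Investigator's overall interpretation will be provided".
- Data listings of all safety assessments, flagged or not (SAP 16.3).

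Protocol 9.6.2.6 schedules ECGs at screening and at Visit 4/early termination only, so each subject has at most one scheduled pair.

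**The concern.** ECG is a named part of the safety objective, and the sample size was set partly to supply a safety database (Protocol 8 and 11.1). QTc is already to be computed two ways and its change summarised. Yet the only numeric classification of individual subjects is a single high limit, in a population aged 9 to 45. A subject who goes from 380 to 470 msec, a rise of 90 msec, meets no numeric rule and enters neither the subject display nor the adverse-event display.

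If the drug produced large rises in a few subjects, a reader of the tables would have no by-arm count of them. SAP 11.3 shows that change from baseline was considered for vital signs: "Vital sign values will be considered PCS if they meet both the observed-value criteria and the change-from-baseline criteria". That contrast is one of stated intent only, because Table 11.3-1, as available for this review, has a single criterion column and no change limits.

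**Working it through.** The documents state no ECG figure to reproduce and give no mean or SD for QTc, QTc change or PR. Those are assumptions, shown as ranges. From the documents: 500 subjects per arm (SAP 14.0), one scheduled postbaseline ECG, and the limits in Table 11.4-1.

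**1. How often would the QTc row be empty?** With normal QTc, p = P(Z > (500 − mean)/SD). The expected count per arm is 500p, and the probability of no case in either arm is (1 − p)^1000. For example, at mean 420 and SD 22, z = 80/22 = 3.64, p = 0.000138, 500p = 0.069 and (1 − p)^1000 = 0.871.

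| Mean (msec) | SD 18 | SD 22 | SD 26 |
|---|---|---|---|
| 400 | > 0.999 | 0.997 | 0.942 |
| 410 | > 0.999 | 0.979 | 0.764 |
| 420 | 0.996 | 0.871 | 0.351 |

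With 400 per arm, the last row's values at SD 22 and 26 become 0.895 and 0.433.

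**2. Would the row respond to a uniform +20 msec shift?** Expected subjects per arm above 500 msec, without and with the shift:

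- mean 400, SD 18: 0.00001 and 0.002
- mean 410, SD 20: 0.002 and 0.12
- mean 420, SD 25: 0.34 and 4.1

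The row is uninformative in the first two cases but not in the third.

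**3. Is the whole ECG table likely to be empty?** PR below 110 msec also counts. Take PR mean 140 to 155, SD 16 to 20 and within-subject correlation 0.7 to 0.9. A bivariate normal, counting only subjects not flagged at baseline, gives 0.6 to 9.9 new cases per arm. The probability of none in either arm is at most 0.28, and is below 0.02 in 11 of the 15 scenarios. QRS and high PR can only add cases. The whole table is therefore unlikely to be empty.

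**4. What would rows based on change show?** With an SD of change of 15 to 22 msec and 500 per arm, the expected counts per arm are:

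| Rise | No effect | Uniform shift |
|---|---|---|
| > 30 msec | 11 to 43 | 46 to 91 (at +10) |
| > 60 msec | 0.02 to 1.6 | 1.9 to 17 (at +20) |

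**5. Uniform shift against a rise in a few subjects.** The SE of the difference in mean change is SD × √(2/500), which is 0.95 msec at SD 15 and 1.39 msec at SD 22.

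- A uniform +10 msec is about 7 to 10 SEs, so the planned means would show it.
- Suppose instead that 2% of the active arm (10 of 500) rise by about 70 msec. The arm mean moves by 0.02 × 70 = 1.4 msec, only about 1.0 to 1.5 SEs. Of those 10, the expected number above +60 is 10 × Φ(10/15) = 7.5 or 10 × Φ(10/22) = 6.8, so about 7. Chance alone would give 0.02 to 1.6.

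**The case against.** The strongest reply is that the plan is not blind to a large rise. In the 380 to 470 msec example, the arm's maximum change would be at least +90, the listings would identify the subject, and an ECG judged clinically significant by the Investigator would have its own display. A uniform effect would be plain in the mean change. Laboratory flags in SAP 11.2 also use limits without change from baseline, and Protocol 11.6.4 asks only for interpretation and shift categories, so SAP 11.4 already goes beyond the protocol. Table specifications sit in a separate document that was not available here.

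All of that stands, and it rules out three stronger conclusions a reader might draw:

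- That the ECG table as a whole will be empty. The PR and QRS rows make this unlikely.
- That a large rise is never flagged or listed. The listings and the Investigator display contradict this.
- That the QTc row will read zero against zero whether or not the drug prolongs QTc. At mean 420 and SD 25 a +20 msec shift gives 4.1 expected cases against 0.34.

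The reply does not supply a count. A maximum describes one subject per arm, listings do not compare arms, and the Investigator's reading is a judgement on the whole ECG with no stated threshold for change.

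**Conclusion.** The point holds as a gap in reporting, not as an error, a contradiction or a missed protocol commitment. No table described in the SAP counts subjects by arm at a QTc level below the 500 msec limit or by the size of the rise. The QTc row, as distinct from the whole ECG table, is probably empty or nearly so in both arms. How probable that is depends on an assumed mean and SD, and the conclusion weakens clearly at the top of the range tried. The practical loss is confined to large rises in a small fraction of subjects, which the mean change would barely register and a categorical count would show. It does not touch the efficacy analyses. It is a cheap improvement, not a necessary correction.

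**What to change.** Before unblinding, add by-arm categorical rows to the ECG summary, separately for QTcF and QTcB, covering lower absolute levels and increases from baseline. Examples are values above 450 and above 480 msec, and increases above 30 and above 60 msec. These cut-offs are not in the documents, and the sponsor should pre-specify and justify its own. Keep above 500 msec as the top category, and extend the subject display and the adverse-event display to the largest-increase category.

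This uses ECGs already scheduled and needs no change in study conduct. The cost is a few extra table rows and some chance flags in both arms, mainly in the lower increase category (about 11 to 43 per arm with no drug effect, under the assumptions above), to be read against placebo.

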11.5 OTHER SAFETY PARAMETERS

11.5.1 Noninflammatory Lesion Counts

Noninflammatory lesions (open and closed comedones) will be counted and recorded in the eCRF and will be analyzed for CFB using an ANCOVA model effects of treatment, (pooled) site, and the baseline value as a covariate using OC data. Note that non-inflammatory lesion counts serve as both a safety and efficacy parameter in this study, reflecting a dual role of assessing efficacy while also evaluating patient safety.

12.0 **HEALTH OUTCOMES ANALYSES**

No health outcome analyses are planned for this study.

13.0 INTERIM ANALYSIS

No interim analysis is planned for this study.

14.0**DETERMINATION OF SAMPLE SIZE**

The sample size was selected to provide an adequate number of subjects to compare the efficacy of sarecycline treatment to placebo and to provide an adequate number of subjects needed for a safety database.

Sample size estimates were calculated for each of the co-primary efficacy endpoints, absolute CFB in facial inflammatory lesion counts and facial IGA success (based on at least 2-point decrease from baseline in IGA score), and the first secondary efficacy endpoint, percent CFB in facial inflammatory lesion counts at Week 12 last observation carried forward (LOCF). The results from a recent study (Study PR-10411) of sarecycline compared to placebo treatment were used to estimate the sample size needed to show a significant difference between the treatments at $\alpha=0.05$ and 90% power using two-sided tests and a 1:1 randomization. It should be noted that one outlier in the data for Study PR-10411 was removed from the estimate for absolute CFB in inflammatory lesion counts in order to provide more accurate estimates for the sample size determination. Results of the calculations and the estimates used in the calculations are provided below:

Continuous Endpoints^a	Sarecycline CFB or %CFB	Placebo CFB or %CFB	Common SD	Sample per Treatment	Total Sample Size
Absolute CFB in inflammatory lesion counts (co-primary)	16	13	12	338	676
Percent CFB in inflammatory lesion counts (secondary)	52%	39%	41%	210	420

a Sample size was based on a two sample t-test of no difference between the treatments

Dichotomous Endpoints^a	Sarecycline Rate	Placebo Rate	Difference in Rates	Sample per Treatment	Total Sample Size
IGA Success (2-point decrease in IGA score from baseline and a score of clear/almost clear; co-primary)	23%	10%	13%	170	340

a Sample size was based on a χ^2 test of no difference between the proportions

While the IGA scale proposed for the Phase 2 study is slightly different than the IGA scale in the Phase 2, the number of subjects to be enrolled (500 per treatment; 1000 total) should provide more than sufficient power for the efficacy evaluations. Additionally, a larger sample is needed in order to provide sufficient numbers of subjects on sarecycline treatment for a safety database.

15.0**STATISTICAL SOFTWARE**

Statistical analyses will be performed using version 9.3 (or newer) of SAS on a LINUX operating system.

16.0

DATA HANDLING CONVENTIONS

16.1

VISIT TIME WINDOWS

Table 16.1–1 presents the visits assigned for efficacy and safety analyses and the corresponding range of treatment days (window) during which an actual visit may occur.

Table 16.1–1. Visit Time Windows

Derived Visit	Scheduled Visit Day^a	Window
Baseline	Day 1	Days \leq 1
Week 3	Day 22	Days [2, 32]
Week 6	Day 43	Days [33, 53]
Week 9	Day 64	Days [54, 74]
Week 12	Day 85	Days \geq 75
End of study ^b	Final or Termination Visit during the treatment period	

a Relative to the date of the first dose of the investigational product or date of randomization if patient did not receive any dose. Day 1 = the date of the first dose of the investigational product (or date of randomization if patient did not receive a dose). There is no Day 0.

b Presented in analysis tables for safety parameters, including but not limited to electrocardiograms, clinical laboratory values, and vital signs.

If the assessment date (if the assessment date is unavailable, using visit date instead) is on or after the date of the first dose of the investigational product, the study day is calculated by assessment date – date of the first dose of the investigational product + 1. If the assessment date is before the date of the first dose of the investigational product, the study day is calculated by assessment date – date of the first dose of the investigational product. Therefore, a negative day indicates a day before the start of the investigational product.

If a subject has 2 or more visits within the same window, the last visit with a nonmissing value will be used for analysis.

16.2

MISSING DATA HANDLING FOR PRIMARY AND SECONDARY EFFICACY ENDPOINTS

For the co-primary and secondary efficacy analyses, the primary missing data imputation method is multiple imputation, as outlined in the following procedures:

- o The SAS PROC MI procedure with a fully conditional specifications (FCS) method will be used to create 20 imputations. The FCS is proposed as it allows for accommodation of categorical variables and it has the versatility to handle arbitrary missing data patterns. Based on these 20 imputations, the relative efficiency will be 0.995 for 10% of missing data and 0.990 for 20% of missing data (Rubin, 1976, 1987, 1996) .

- For inflammatory lesion counts, if any of the subtypes (papules, pustules, and nodules/cysts) is missing, the inflammatory lesion count is missing. The variables included in the imputations are age, gender, and the measurements of the corresponding endpoint count) at baseline, Week 3, Week 6, Week 9, and Week 12.
- For IGA, the raw scores will be used for the imputation. The variables included in the imputations are age, gender, and the measurements of the endpoint at baseline, Week 3, Week 6, Week 9, and Week 12.
- All imputations will be performed by treatment group based on the randomized study medication and based on the randomized gender strata. The number of imputation is set at 20 with number of 50 burn-in iterations. The seed used for imputation for all endpoints is [REDACTED]. The logistic regression model for gender is based on the probability of female. For age, IGA raw scores and lesion counts, regression with predictive mean matching method will be used. The imputed values will be rounded to the nearest integer for IGA and lesion counts.
- The following are the SAS programs used to impute IGA at week 12:

The following SAS program will be used to impute inflammatory and non-inflammatory lesion counts at week 12.

- An analysis of covariance (ANCOVA) model for inflammatory lesion counts and a CMH analysis for the IGA success as stated in Sections 10.1.1 and 10.1.2, respectively, will be performed for each of the imputed dataset.
- An analysis of covariance (ANCOVA) model for inflammatory and non-inflammatory lesion counts as stated in Section 10.2 will be performed for the imputed dataset for the secondary endpoints.
- The SAS PROC MIANALYZE procedure will be used to produce final parameter estimates, including the point estimates and standard errors, adjusted treatment differences, confidence intervals and p-values for the primary and secondary variables.
- For the CMH test, the Wilson-Hilferty transformation (Wilson & Hilferty, 1931, O'Kelly & Ratitch, 2014) will be used. Under the null hypothesis, the transformed statistic is approximately normally distributed:

$$wh_CMH^{(m)} = \sqrt[3]{\frac{cmh^{(m)}}{k}} \sim normal\left(1 - \frac{2}{9k}, \frac{2}{9k}\right)$$

Where $cmh^{(m)}$ is the chi-square statistics each with k degrees of freedom from $m = 1, \dots, M$ imputed datasets. In this case, $k=1$. This statistic will be passed to PROC MIANALYZE to obtain the combined p-value for CMH test.

The same method will be used to obtain the p-values from the Breslow-Day test.

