9.4 Study Treatments

9.4.1 Treatments Administered

Subjects meeting the eligibility requirements will be randomized in a 1:1 ratio to receive either active sarecycline tablets or placebo tablets administered orally as 60 mg, 100 mg or 150 mg of sarecycline or matching placebo tablets based on the subject's body weight.

Subjects will ingest one tablet daily at approximately the same time each day, at least 1 hour prior to, or 2 hours after eating.

9.4.1.1 Subjects Participating in PK Schedule 3

Subjects who participate in PK Schedule 3 will receive one dose of active study treatment at Visit 4 (Week 12) regardless of randomized study treatment (active or placebo) after all visit assessments are completed. The study treatment will be adjusted to the subject's body weight on the visit date.

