9.6.2.5 Vital Signs

Vital signs will be measured at screening (SV1 and SV2) and at each treatment period visit and at Visit 4/ET **and Visit 5 (for subjects participating in PK Schedule 3)**.

Vital signs at screening will include oral or auricular temperature, heart rate, systolic and diastolic blood pressure (with the subject seated for at least 5 minutes prior to measurement). Only blood pressure and heart rate will be recorded at treatment period visits.

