Subjects who are in PK Schedule 3 will be instructed not to take their dose on the day of their Visit 4/Week 12. Instead, subjects will be dosed in clinic with active study treatment after all visit assessments are done. Make all efforts to schedule the visit to accommodate the subjects' routine schedule of dosing. For example, if the subject regularly takes the drug at night, an afternoon visit is preferable for PK sampling. In case it is not possible to schedule an afternoon appointment, a minimum of 12 hours should elapse between the dose taken at the visit and the previous dose.

Subjects will have a follow-up visit (Visit 5/Week 13) 1 week after Visit 4 as described in Section 9.5.2.6.

Table 9-7 Sampling Times for PK Schedule 3

Visit	Sample Time
Visit 1 (Week 3 \pm 3 days)	At any time during the visit
Visit 4 (Week 12 \pm 3 days)	(1) Postdose: Between 0.5 hours and 1 hour after dose administration (2) Postdose: Between 1.5 hours and 2 hours after dose administration (3) Postdose: Between 3 hours and 4 hours after dose administration

Blood samples will be collected, processed, stored, and shipped as described in [Appendix 3](#).

Diary for Recording Dose Administrations for PK Analysis

For subjects participating in PK Schedule 1, PK Schedule 2, **and PK Schedule 3**, a diary will be dispensed at Screening Visit 2/Baseline and at Visit 3/Week 9, the visits prior to PK sampling. The subjects participating in PK sampling will be instructed to record the dose administration times for the 2 doses taken prior to Visit 1/Week 3 and Visit 4/Week 12 in the diary and on the day of Visit 4/Week 12.

The subjects participating in PK sampling will be instructed to record the dose administration times for the 2 doses taken prior to Visit 1/Week 3 in the diary.

During Visit 1/Week 3 and Visit 4/Week 12, the responsible personnel at the site will review and collect the pages from the subjects' diary. The dose date and time will be recorded in the eCRFs.

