11.1 ADVERSE EVENTS

Adverse events will be coded by system organ class and preferred term using the *Medical Dictionary for Regulatory Activities*, version 18.0 or newer.

Adverse events with onset on or after the first dose date of the study drug will be considered as “treatment-emergent adverse event (TEAE)”. An AE that occurs more than 30 days after the date of the last dose of the investigational product will not be counted as a TEAE. Adverse events summaries will present the number and percentage of subjects reporting an adverse event by treatment and overall as well as the number of events reported. The denominators for calculating the percentages by treatment will be based on the number of subjects exposed in the Safety population to each treatment and overall. The treatment will be based on the double-blind treatment received. For subjects who are in PK schedule 3, the TEAE summary described will comprise data prior to the active dose taken at the Week 12 visit. Further adverse events experienced after this Week 12 dose will be listed separately for these subjects.

The number and percentage of subjects reporting TEAEs in each treatment group and overall will be tabulated by system organ class and preferred term and further categorized by severity and relationship to study treatment. If more than 1 AE is coded to the same preferred term for the same subject, the subject will be counted only once for that preferred term using the greatest severity and strictest causality for the summarization by severity and relationship.

The incidence of common ($\geq 2\%$ of subjects in any treatment group) TEAEs will be summarized by preferred term and treatment group and will be sorted by decreasing frequency for sarecycline treatment group.

The total number of TEAEs by severity and relationship to study treatment will be summarized by treatment group.

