16.3 REPEATED OR UNSCHEDULED ASSESSMENTS OF SAFETY PARAMETERS

If a subject has repeated assessments before the start of investigational product, the results from the final nonmissing assessment made before the start of the investigational product will be used as baseline. If end-of-study assessments are repeated or if unscheduled visits occur, the last nonmissing postbaseline assessment will be used as the end-of-study assessment for generating summary statistics. However, all postbaseline assessments will be used for PCS value determinations, and all assessments will be presented in the data listings.

16.4**MISSING DATE OF THE LAST DOSE OF INVESTIGATIONAL PRODUCT**

When the date of the last dose of the investigational product is missing for a subject in the Safety Population, all efforts should be made to obtain the date from the Investigator. If after all efforts are made it is still missing, the last available dosing record date will be used as the last dose date.

16.5**MISSING SEVERITY ASSESSMENT FOR ADVERSE EVENTS**

If severity is missing for an AE that started before the date of the first dose of the investigational product, an intensity of mild will be assigned. If severity is missing for an AE that started on or after the date of the first dose of the investigational product, an intensity of severe will be assigned. The imputed values for severity assessment will be used for the incidence summary; the values will be shown as missing in the data listings.

16.6**MISSING RELATIONSHIP TO INVESTIGATIONAL PRODUCT FOR ADVERSE EVENTS**

If the relationship to study treatment is missing for an AE that started on or after the date of the first dose of the investigational product, a relationship of related will be assigned. The imputed values for relationship to study treatment will be used for the incidence summary; the values will be shown as missing in the data listings.

16.7**MISSING DATE INFORMATION FOR ADVERSE EVENTS**

The following imputation rules only apply to cases in which the start date for AEs is incomplete (ie, partly missing).

Missing month and day

- If the year of the incomplete start date is the same as the year of the first dose of the investigational product, the month and day of the first dose of the investigational product will be assigned to the missing fields
- If the year of the incomplete start date is before the year of the first dose of the investigational product, *December 31* will be assigned to the missing fields

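### For PK Schedule 3 subjects, the SAP's visit windows put Visit 5 blood pressure, heart rate and weight, taken after an in-clinic active dose, into the Week 12 summaries by double-blind arm

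*SAP*

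**What the plan says.** **Windows.** SAP 16.1 (Table 16.1-1) applies one set of visit windows to efficacy and safety. Week 12 is scheduled for Day 85 and takes every day from Day 75, with no upper limit. There is no Week 13 or Visit 5 row. The tie rule is: "If a subject has 2 or more visits within the same window, the last visit with a nonmissing value will be used for analysis".

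**Dose at Visit 4.** Under Protocol 9.4.1.1, each PK Schedule 3 subject "will receive one dose of active study treatment at Visit 4 (Week 12) regardless of randomized study treatment (active or placebo"). Protocol 9.6.3.4 fixes the order: "subjects will be dosed in clinic with active study treatment after all visit assessments are done". The Visit 4 values therefore precede that dose.

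**Visit 5.** Protocol 9.5.2.6, 9.6.2.4 and 9.6.2.5 have these subjects return at Week 13 (± 3 days) for blood pressure, heart rate and weight.

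**Reporting.** SAP 11.3 summarises vital signs, including weight, by treatment group at each visit and at the end of the double-blind period. Protocol 11.6.5 also reports vital signs by double-blind treatment and visit.

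**Where the plan already separates post-dose data.** For treatment-emergent adverse events, SAP 11.1 says "the TEAE summary described will comprise data prior to the active dose taken at the Week 12 visit". The same section removes later SAEs, and SAP 9.1 lists the single active dose apart from double-blind exposure. No such rule is given for vital signs or weight.

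**The concern.** A table headed by double-blind arm should hold values obtained under double-blind treatment. For PK Schedule 3 subjects the Visit 4 measurement is that value. The window and tie rule together replace it with one taken a week later. For a placebo subject, the substituted value follows an active dose. For a sarecycline subject, it is taken about a week after the last dose, so it is no longer an on-treatment value.

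The SAP accepts the principle of cutting data at this dose for adverse events, SAEs and exposure. Vital signs and weight are the numeric safety measures scheduled at Visit 5, and they have no such cut. At stake are the Week 12 descriptive safety tables and, depending on how a programmer reads conflicting text, individual PCS flags counted under placebo.

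**Working it through.** **1. Reproduce the SAP's scheduled days.** With Day 1 as the first dose and no Day 0, scheduled day = 7 × week + 1. Weeks 3, 6, 9 and 12 give 22, 43, 64 and 85, as in Table 16.1-1.

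**2. Place the two visits.**
- Visit 4 (Week 12 ± 3 days): 85 ± 3 = Days 82 to 88.
- Visit 5 (Week 13 ± 3 days): 7 × 13 + 1 = 92, so Days 89 to 95.

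**3. Map to windows.** Weeks 3, 6 and 9 cover Days 2–32, 33–53 and 54–74; Week 12 covers Day 75 onward. All 14 days from 82 to 95 fall in Week 12. Visit 5 is always the later visit, so the tie rule selects it whenever its value is nonmissing.

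**4. Test whether an upper limit would cure it.** Weeks 6 and 9 use ± 10 days (43 ± 10 = 33–53; 64 ± 10 = 54–74). The same for Week 12 gives 85 ± 10 = [75, 95], which still contains all of Days 89 to 95. If Visit 5 is instead counted as 7 ± 3 days after the actual Visit 4, it runs from 82 + 4 = 86 to 88 + 10 = 98; only Days 96 to 98 would drop out. The causes are the missing Week 13 row, the last-visit rule and the missing cut at the active dose.

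**5. Set the other vital-sign rules side by side.**

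| Source | Points toward |
|---|---|
| SAP 11.3: end-of-period, shift and PCS tables refer to the double-blind period, with no cut-off defined | Excluding Visit 5 |
| SAP 16.3: "all postbaseline assessments will be used for PCS value determinations" | Including Visit 5 in PCS |
| SAP Table 16.1-1, End of study row: final or termination visit in the treatment period; its footnote names vital signs | Including Visit 5 |
| Schedule of events (Protocol Appendix 1, SAP Table 4–1): Visit 5 is under the Treatment Period heading | Including Visit 5 |
| Protocol 9.5.2.5 and 9.5.2.6: these subjects complete the Termination Form at Visit 5, not Visit 4 | Including Visit 5 |

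For these tables the text conflicts; it does not settle the matter either way.

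**6. Size.** The documents do not give the number of PK Schedule 3 subjects (N), so a range is assumed. With a 1:1 split and about 500 per arm (Protocol 9.3), placebo share = (N/2)/500, and the shift in the placebo mean = share × change per subject. A change of 5 units per subject is also an assumption.

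| Assumed N | Placebo subjects | Share of arm | Mean shift at 5 units each |
|---|---|---|---|
| 5 | 2.5 | 0.5% | 0.025 |
| 10 | 5 | 1% | 0.05 |
| 20 | 10 | 2% | 0.1 |
| 50 | 25 | 5% | 0.25 |
| 100 | 50 | 10% | 0.5 |

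**The case against.** The strongest reply is that SAP 11.3 already confines the end-of-period, shift and PCS tables to the double-blind period. Treatment lasts 12 weeks, the extra dose is a known active dose given after the Visit 4 assessments, and SAP 9.1 keeps it apart from double-blind exposure. The natural reading puts Visit 5 outside. The last-value rule in SAP 16.3 also applies to repeated end-of-study assessments and unscheduled visits, and Visit 5 is a scheduled visit. This stands in part: a reader might infer that Visit 5 values definitely become end-of-study values and PCS flags, and the documents do not support that. They support only an unresolved conflict. The reply does not reach the by-visit Week 12 summary, for which no text exempts Visit 5.

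A second reply is that table specifications sit in a separate document (SAP 4.0) that may label Visit 5 on its own. That is possible, but it would depart from the SAP's stated window rule.

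A third is that no Visit 4 data are lost, since SAP 16.3 puts all assessments in the listings. This is correct. The Visit 4 value is displaced from the summary, not from the record.

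**Conclusion.** The point holds, at minor severity. Displacement is certain under the written rules only for the by-visit Week 12 summaries of blood pressure, heart rate and weight, and only for PK Schedule 3 subjects with a nonmissing Visit 5 value. For the end-of-period, shift and PCS vital-sign tables, SAP 11.3, SAP 16.3, Table 16.1-1 and the schedule must be reconciled.

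Three broader readings are tempting but unsupported.
- *The safety tables by arm are contaminated in general.* Laboratory tests, ECG, IGA and lesion counts are not scheduled at Visit 5, and TEAEs, SAEs and exposure are handled separately. Efficacy is untouched.
- *The open-ended window is the cause.* A [75, 95] window would still take in Visit 5 on its scheduled days.
- *The effect is material for ages 9 to 11.* That age band appears only in the demographic summary (SAP 8.0); no safety summary is planned for it, and the number of PK Schedule 3 subjects is not given.

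The effect on arm means is probably small: 0.025 to 0.5 units over the assumed range of 5 to 100 subjects, if each value moved by 5 units. The documents do not say how far any value would move. SAP 11.3 plans descriptive summaries of vital signs and no inferential test. An individual PCS flag attributed to the wrong exposure is the more visible risk.

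**What to change.** State in SAP 16.1, 16.3 and 11.3 that, for PK Schedule 3 subjects, assessments after the Visit 4 in-clinic active dose are excluded from the Week 12 window, from end-of-study and end-of-double-blind values, from shift tables and from PCS counts, and are listed separately, as SAP 11.1 does for adverse events. An upper limit on the Week 12 window should not be used in place of this cut.

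The cost is one sentence with cross-references and one programming condition. Nothing is lost, because the Visit 5 values remain in the listings.
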